1.5.2 Pediatric Population

Enrollment is limited to subjects who experienced virologic failure associated with 1 or more treatment-emergent RASs present at 12 weeks after receiving GZR treatment in prior treatment study PN079.

1.6 DOSAGE/DOSAGE FORM, ROUTE, AND DOSE REGIMEN

No treatments will be administered.

1.7 STUDY FLOW CHART

There are 2 flow charts for this study, 1 for adult subjects and 1 for pediatric subjects. The subject's age at the time of entering the prior treatment study will be used for PN017 procedures.

1.7.1 Adult Population

Visit No.	1 ⁸	2	3	4	5	6	7	8 ¹³	9 ¹³	10 ¹³	11 ¹³	12
	Year 1		Year 2		Year 3		Year 4		Year 5			
STUDY PROCEDURES ¹	Screen/ Baseline ⁴	Mo. 6	Mo. 12	Mo. 18	Mo. 24	Mo. 30	Mo. 36 ¹¹	Mo. 42	Mo. 48	Mo. 54	Mo. 60 ¹¹	(Unscheduled) Viral Confirmation Visit ¹⁰
Informed Consent	X											
Informed Consent for FBR ²	X											
Provide Subject Identification Card	X											
Medical History ¹²	X											
Inclusion/Exclusion Criteria	X											
CLINICAL EVALUATIONS												
Directed Physical Examination (PE)	X		X		X		X		X		X	X
Child-Pugh score computation	X		X		X		X		X		X	X
Blood pressure (systolic and diastolic) and heart rate	X		X		X		X		X		X	X
Weight	X		X		X		X		X		X	
Height	X											
Review procedure related AEs, ECIs, and drug-related SAEs ³	X	X	X	X	X	X	X	X	X	X	X	X
LABORATORY SAFETY EVALUATIONS												
Chemistry, hematology, and coagulation panel	X	X	X		X		X		X		X	X
MELD score (with and without dialysis)	X		X		X		X		X		X	X
Fibrosure® (Fibrotest®)		X	X		X		X		X		X	X
eGFR (if prior treatment study was PN052)	X		X		X		X		X		X	X
HCV EVALUATIONS												
HCV RNA Level ⁵	X	X	X	X	X	X	X	X	X	X	X	X
Viral Resistance and Biomarker ⁶	X	X	X	X	X	X	X	X	X	X	X	X
Blood (DNA) for FBR ⁷	X											
Blood (Plasma) for FBR ⁷	X											
HCV Genotype ⁹	X											X

Visit No.	1 ⁸	2	3	4	5	6	7	8 ¹³	9 ¹³	10 ¹³	11 ¹³	12
	Year 1		Year 2		Year 3		Year 4		Year 5			
STUDY PROCEDURES ¹	Screen/ Baseline ⁴	Mo. 6	Mo. 12	Mo. 18	Mo. 24	Mo. 30	Mo. 36 ¹¹	Mo. 42	Mo. 48	Mo. 54	Mo. 60 ¹¹	(Unscheduled) Viral Confirmation Visit ¹⁰
AE=adverse event; DNA=deoxyribonucleic acid; ECI- event of clinical interest; eGFR=estimated glomerular filtration rate; FBR=future biomedical research; HCV=hepatitis C virus; MELD=Model for End Stage Liver Disease; Mo.=month; RNA=ribonucleic acid; SAE=serious adverse event												
¹ Visits should be scheduled as close to the indicated study period as possible. Visit windows are +/- 3 months. All visits should be recorded on the actual date that they occur and any missed or late visits must be documented accordingly. ² Participation in FBR is voluntary and is not required in order to participate in the study. ³ Protocol specified ECIs, AEs related to protocol-specified procedures (blood draw), and drug related new Serious Adverse Events, which occur following enrollment in the present study (after Informed Consent Form is signed) will be reported. ⁴ If a subject is directly entered into this long-term follow-up protocol on the same day as the last study day of the prior treatment study, since these visits have different laboratory requirements, the lab kit for each of the two visits must be used. Samples are collected for each study separately at the same visit. (See section 3.2.4.1) ⁵ Subjects who achieved SVR in previous study and who are tested in this study and found to have HCV RNA \geq 1000 IU/mL, will have their Viral Resistance sample tested. ⁶ HCV sequence analysis will be performed, as appropriate, and will depend on the HCV-RNA level results. ⁷ Informed consent for future biomedical research samples must be obtained before the DNA and plasma samples are collected. ⁸ The screening visit should occur within 3 months of the last visit of the previous protocol. ⁹ Subjects who had HCV RNA < LLoQ at the end of follow-up in the original treatment protocol and who are tested and have HCV-RNA \geq LLoQ during this study will have their HCV Genotype obtained. If a subject has HCV RNA \geq LLoQ at Visit 1, an HCV Genotype must be performed at that visit. ¹⁰ If the unscheduled visit is being performed for follow-up of an AE/SAE (as defined in this protocol), a directed physical exam and safety labs should also be performed at this visit. ¹¹ For subjects in the 3 year follow-up who discontinue early, a Visit 7 (Month 36) Visit should be completed as the early discontinuation visit. For subjects in the 5 year follow-up (eg. PN052) who discontinue early, a Visit 11 (Month 60) visit should be completed as the early discontinuation visit. ¹² Refer to Section 3.2.4.1 for required medical history. ¹³ Visits 8, 9, 10, and 11 will only be performed if subjects were in PN052 as their parent study.												

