3.2.4.1 Screening/Baseline Visit (Visit 1)

Within 3 months of the last visit (e.g. FW24) of their prior treatment study, potential subjects will be evaluated to determine if they fulfill the Inclusion/Exclusion entry requirements as described in Sections 2.2 and 2.3, respectively. The investigator will discuss with each potential subject the nature of the study, its requirements, and its restrictions. Informed consent/assent, as described below, must be obtained prior to initiation of any screening/baseline procedures or evaluations.

All procedures must be completed and subject eligibility confirmed by the investigator prior to the subject receiving an allocation number by the study site.

Electronic transfer of data from the prior treatment study will occur for the following data:

- Dosage and length of therapy (start date/end date) of GZR from the prior treatment study
- All HCV RNA
- Date declared relapse in prior treatment study (if applicable)
- HCV Genotype

- All sequence analysis
- All laboratory results:
 - Hemoglobin
 - Hematocrit
 - Red Blood Cell Count
 - Total White Blood Cell count
 - Lymphocytes
 - Neutrophils
 - Platelet Count
 - ALT
 - AST
 - Creatinine
 - eGFR (if prior treatment study was PN052)
 - Alkaline phosphatase
 - Total Bilirubin (direct and indirect)
 - Urea nitrogen
 - Total Protein
 - Albumin
 - Glucose
 - Coagulation panel: PT, INR and aPTT

In addition, the following information will be collected at the screening/baseline visit and must be manually entered into the data collection system:

- Protocol number and subject allocation number from the prior treatment study.
- Name, dosages and length of therapy (start date/end date) of all other HCV therapies including other research protocols or standard of care.
- For adult subjects, the following medical history terms, which occurred after the prior treatment study and before study entry, will be collected:
 - Spontaneous bacterial peritonitis;
 - Variceal bleeding;
 - Ascites;
 - Encephalopathy;
 - Hepatorenal syndrome;
 - Hepatocellular carcinoma (collected as an ECI);
 - Change in chronic kidney disease as assessed by eGFR (collected as an ECI);
 - Liver transplant;
 - Kidney transplant (PN052 subjects; collected as an ECI);
 - New onset diabetes, cryoglobulinemia, cardiovascular disease limited to new onset angina, myocardial infarction, or neurologic disorders limited to transient ischemic attack (TIA) or stroke;

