3.4.3.2 Events of Clinical Interest

3.4.3.2.1 Adult Population

ECIs will be recorded on the AE CRFs/Worksheets. ECIs defined for this protocol include:

- Spontaneous bacterial peritonitis;
- Variceal bleeding;
- Ascites;
- Encephalopathy;
- Hepatorenal syndrome;
- Hepatocellular carcinoma; - Any hepatocellular carcinoma that occurred and was not previously reported in the prior treatment study should be reported as an ECI;
- Liver transplant;
- Kidney transplant (PN052 subjects only) – any kidney transplant that occurred and was not previously reported in the prior treatment study should be reported as an ECI;
- Decreased eGFR calculated by the Modification of Diet in Renal Disease equation (PN052 subjects) will be analyzed for change from baseline in PN052;
 - For this study a decrease in eGFR is defined for subjects not on dialysis as:
 - CKD4 (15 to 30 ml/min/1.73 m²) in PN052 and is now CKD5 (<15 ml/min/1.73 m²),
 - CKD5 without dialysis in PN 052 and is now CKD5 with dialysis, OR
 - CKD4 in PN 052 and initiates dialysis
- New onset diabetes (PN052 subjects only);
- Cryoglobulinemia (PN052 subjects only);
- Cardiovascular disease limited to angina and myocardial infarction;
- Neurologic disorders limited to TIA or stroke;
- Graft rejection in subject who has undergone liver or kidney transplantation; or
- Post transplantation glomerulonephritis (PN052 subjects only).

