3.5.5.2 Statistical Methods for Safety Analyses

3.5.5.2.1 Adult Population

Safety and tolerability in adult subjects will be assessed by clinical review of all relevant parameters including drug-related SAEs, ECIs, and laboratory parameters.

The number and proportion of subjects with ECIs will be tabulated. Continuous laboratory parameters will be summarized by 12-month intervals using descriptive statistics. These 12-months intervals are related to the Study Months and are determined by a set of continuous relative day ranges, calculated from study entry. Day ranges for safety evaluation are provided in [Table 8](#).

Table 8

Definition of Study Months for Safety Evaluation

Month	Relative Day Range ^a
Screening/Baseline	-91 to 30
12	-31 to 547
24	548 to 912
36	913 to 1277
48	1278 to 1642
60	≥1643

^a Day range relative to study entry, i.e. date of screening/baseline visit

Yearly changes from baseline in MELD and Child-Pugh scores will be summarized in all adult subjects using descriptive statistics. Changes in eGFR will be summarized for subjects from PN052. Descriptive statistics will be provided for the rate that subjects with CKD (PN052) require liver and/or kidney transplants.

Missing values will be handled using the Data-As-Observed approach.

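### HCC, PN052 kidney transplant and eGFR change from before PN017 entry are ECIs while other pre-entry events are medical history, and the ECI and transplant summaries set no onset window

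*Combined protocol and SAP*

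**What the plan says.** Four places bear on which events count as ECIs and how they are summarised in adults.

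- **Section 1.7.1, footnote 3.** It lists protocol-specified ECIs, procedure-related AEs and new drug-related SAEs, "which occur following enrollment in the present study (after Informed Consent Form is signed) will be reported".
- **Section 3.2.4.1, Visit 1.** For adults, "the following medical history terms, which occurred after the prior treatment study and before study entry, will be collected". Three items in the list carry an ECI mark: "Hepatocellular carcinoma (collected as an ECI"), "Change in chronic kidney disease as assessed by eGFR (collected as an ECI") and "Kidney transplant (PN052 subjects; collected as an ECI"). The rest carry none, beginning with "Spontaneous bacterial peritonitis". They are variceal bleeding, ascites, encephalopathy, hepatorenal syndrome, liver transplant, new-onset diabetes, cryoglobulinemia, angina or myocardial infarction, TIA or stroke, graft rejection and post-transplant glomerulonephritis.
- **Section 3.4.3.2.1, ECI definitions.** "Any hepatocellular carcinoma that occurred and was not previously reported in the prior treatment study should be reported as an ECI". Kidney transplant has the same look-back, for PN052 subjects only. The eGFR event is defined by a change from the subject's status in PN052. No other event has a look-back.
- **Section 3.5.5.2.1, analysis.** "The number and proportion of subjects with ECIs will be tabulated". The section also plans descriptive statistics on how often PN052 subjects need a liver and/or kidney transplant.

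Section 3.5.4.2.1 puts all data from consenting adults into the safety evaluation. Section 3.5.5.4 summarises medical history with the baseline characteristics.

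**The concern.** A site that follows footnote 3 would not report an HCC from the gap as an ECI; a site that follows Section 3.4.3.2.1 must. The same kind of event could therefore be classified differently at different sites.

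Even if every site follows Section 3.4.3.2.1, the ECI table has an uneven time window. An HCC that was present at entry counts in the numerator, while ascites or a variceal bleed from the same weeks does not. An event already present at entry cannot be incident on study. Exploratory objective 4 names HCC, transplantation and the decompensation events together, and long-term safety is a primary adult objective, so readers will naturally set these proportions side by side. The PN052 transplant summary has the same problem if it is built from ECI records: a kidney transplant in the gap is an ECI, and a liver transplant in the gap is not.

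**Working it through.** The plan gives no event rate, event count or sample-size basis on this point, so there is no figure of its own to reproduce. The check is a comparison of the text, followed by the size of the window difference.

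**1. How an event in the gap is classified**

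| Gap event | Footnote 3 | Section 3.2.4.1 | Section 3.4.3.2.1 |
|---|---|---|---|
| HCC (all adults) | outside the ECI window | marked as ECI | ECI unless reported in the prior study |
| Kidney transplant (PN052) | outside | marked as ECI | ECI unless reported in the prior study |
| eGFR change (PN052) | outside | marked as ECI | defined against PN052 status |
| All other listed events | outside | no ECI mark | no look-back |

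The first three rows conflict across columns. The last row does not, and that is the asymmetry. Kidney transplant and eGFR are PN052-only ECIs, so of the three marked events only HCC affects all adults.

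**2. Whether the analysis section removes the difference**

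Section 3.5.5.2.1 gives no onset condition, person-time denominator or split at entry for ECIs. The day ranges in Table 8 are introduced for the 12-month laboratory summaries and are not applied to ECIs in the text. With all data from consenting adults included, a gap HCC recorded as an ECI enters the table. A gap decompensation event goes to the medical-history summary.

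**3. Size of the window difference**

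Inputs: the gap is at most 3 months (inclusion criterion 2); planned follow-up is 36 months, or 60 months for PN052 (Section 2.4.1.1).

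- Extra window relative to follow-up, gap / follow-up: 3/36 = 8.3%; 3/60 = 5.0%.
- Pre-entry share of the longer window, gap / (gap + follow-up): 3/39 = 7.7%; 3/63 = 4.8%.

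With one common window for every event type, the difference is 0 months.

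**4. Effect on a reported proportion (illustration)**

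The documents give no event rates, so constant rates of 0.5, 1 and 3 per 100 person-years are assumed. Proportion = 1 − exp(−rate × time).

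| Assumed rate per 100 person-years | 36 months | 39 months | 60 months | 63 months |
|---|---|---|---|---|
| 0.5 | 1.49% | 1.61% | 2.47% | 2.59% |
| 1 | 2.96% | 3.20% | 4.88% | 5.11% |
| 3 | 8.61% | 9.29% | 13.93% | 14.57% |

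For example, at 1 per 100 person-years: 1 − exp(−0.01 × 3) = 2.96% and 1 − exp(−0.01 × 3.25) = 3.20%. These are upper-end differences, since they give every subject the full 3-month gap.

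**The case against.** The strongest reply is that the gap rule is a deliberate exception and the flow chart leads to it. Footnote 3 belongs to the row for reviewing AEs, ECIs and SAEs. The medical-history row carries footnote 12, which sends the reader to Section 3.2.4.1, where the marked events are listed. The summary of changes explains that the HCC look-back was meant to capture events between the two studies. Footnote 3 could also be read so that its time limit governs only the drug-related SAEs, although the comma before the clause makes that less natural. Finally, the plan has no hypothesis tests, no person-time ECI rates and no planned comparison between event types. Follow-up already varies between subjects, and no gap event on the list goes uncollected.

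Much of this stands. It explains why gap events are collected, and it means that no formal inference is damaged. It does not say which onset window the ECI table or the PN052 transplant summary uses, and the uneven treatment of event types remains under either reading of footnote 3.

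A reader might infer a much larger effect. Section 3.5.5.1.1 allows screening up to 1 year after last dose for subjects enrolled before AM 03. Subtracting 24 weeks leaves 365.25 − 168 = 197 days, about 6.5 months. That would add 6.5/36 = 18% to the window, or 6.5/12 = 54% and 6.5/6 = 108% for responders stopped after 12 or 6 months. The documents do not support these figures. Follow-up week 24 is given only as an example of the last prior visit. The summary of changes places the HCC look-back in Amendment 04, whereas responders outside PN052 were discontinued under AM 03, and nothing says that the look-back was applied to them retrospectively.

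Nor should the point be framed as HCC after cure. Section 2.2 limits new adult enrolment since AM 03 to subjects who failed therapy, although Section 1.5.1 also admits PN052 subjects.

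**Conclusion.** The point holds as a modest one about definition and interpretability. Footnote 3 conflicts with Sections 3.2.4.1 and 3.4.3.2.1, and the ECI table as specified mixes pre-entry and on-study events for HCC and the PN052 kidney events only. The PN052 transplant summary is affected if it draws on ECI records, which the plan does not state.

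Under the current entry window the excess is at most 3 months, about 8% of 36 months or 5% of 60. At an assumed 1 per 100 person-years it moves a 36-month proportion from 2.96% to at most 3.20%. The effect could be larger for subjects with short follow-up or entry before AM 03, but how much larger depends on assumptions that the documents do not settle. The eGFR event is a separate case: it is cumulative from PN052 by definition, so its reference point can lie further back than the gap.

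**What to change.** 1. Reconcile footnote 3 with Sections 3.2.4.1 and 3.4.3.2.1, so that it is clear which gap events are recorded as ECIs. Collection stays unchanged.
2. In Section 3.5.5.2.1, tabulate ECIs with onset after PN017 consent, using the same window for every event type.
3. Show all gap events in a separate between-studies table: those marked as ECIs and every medical-history term listed in Section 3.2.4.1, non-hepatic terms included. Leaving out the non-hepatic terms would keep part of the asymmetry.
4. Report the eGFR event separately as change from PN052 status, and identify transitions already present at Visit 1. With eGFR measured yearly, a laboratory-defined onset cannot be dated precisely against consent, so a plain onset filter would not suit this event.
5. Apply the same split to the PN052 liver and kidney transplant summary.

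The cost is SAP wording and one table split by onset date. ECIs go on the AE forms (Section 3.4.3.2.1), for which start dates are recorded (Table 6). The Visit 1 medical-history terms belong to the gap by definition. No new data are needed.

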1.7.2 Pediatric Population

Visit No.	1 ⁵	2	3	4	5	6	7	Unscheduled Visit ⁶	
	Year 1		Year 2		Year 3				
	Screen/Baseline ⁴	Mo. 6	Mo. 12	Mo. 18	Mo. 24	Mo. 30	Mo. 36 ⁷		
STUDY PROCEDURES¹									
Informed Consent/Assent	X								
Informed Consent/Assent for FBR ²	X								
Provide Subject Identification Card	X								
Inclusion/Exclusion Criteria	X								
Medical History	X								
CLINICAL EVALUATIONS									
Directed Physical Examination	X		X		X		X	X	
Weight	X		X		X		X	X	
Height	X		X		X		X	X	
Date of menarche (females only)	X	X	X	X	X	X	X		
Procedure Related AEs and drug-related SAEs ³	X	X	X	X	X	X	X	X	
HCV EVALUATIONS									
HCV RNA Level and sequence analysis ⁸	X	X	X	X	X	X	X	X	
Viral Resistance and Biomarker ⁸	X	X	X	X	X	X	X	X	

AE=adverse event; DNA=deoxyribonucleic acid; FBR=future biomedical research; HCV=hepatitis C virus; Mo.=month; RNA=ribonucleic acid; SAE=serious adverse event

1 Visits should be scheduled as close to the indicated study period as possible. Visit windows are +/- 3 months. All visits should be recorded on the actual date that they occur and any missed or late visits must be documented accordingly.
 2 Participation in FBR is voluntary and is not required in order to participate in the study.
 3 AEs related to protocol-specified procedures (blood draw) and drug related new Serious Adverse Events, which occur following enrollment in the present study (after Informed Consent Form is signed) will be reported.
 4 If a subject is directly entered into this long-term follow-up protocol on the same day as the last study day of the prior treatment study, only the lab kit from prior treatment study needs to be used.
 5 The screening visit should occur within 3 months of the last visit of the previous protocol.
 6 If the unscheduled visit is being performed for follow-up of an AE/SAE (as defined in this protocol), only a directed physical exam is needed at this visit. If for follow-up of viral resistance, only HCV evaluations are needed.
 7 For subjects who discontinue early, a Visit 7 (Month 36) should be completed as the early discontinuation visit.
 8 Leftover main study plasma from HCV RNA and resistance will be stored for FBR if the subject/legally acceptable representative consents to FBR.

2. CORE PROTOCOL

2.1 OBJECTIVES AND HYPOTHESES

2.1.1 Primary

2.1.1.1 Adult Population

In HCV-infected subjects who received at least 1 dose of GZR in a previous study:

1. **Objective:** To evaluate the durability of response in subjects who achieved SVR₂₄ in the prior treatment study and at the time of entry into PN017 were HCV ribonucleic acid (RNA) <lower limit of quantification (LLoQ) (either target not detected [TND] or target detected, unquantifiable [TD(u)]).
2. **Objective:** To evaluate the presence of treatment-emergent antiviral resistance to NS3/4A, NS5A and/or NS5B regions, (as applicable) and determine if there is a reversion to wild-type pattern within the 3-year time frame of this long-term follow-up study (or 5-year time frame for subjects from PN052) in subjects with virologic failure in the prior treatment study and with HCV RNA ≥ 1000 IU/mL in Protocol 017.
3. **Objective:** To evaluate the long-term safety.

2.1.1.2 Pediatric Population

In HCV-infected subjects who received at least 1 dose of GZR in a previous study:

1. Objective: To evaluate the persistence of treatment-emergent antiviral resistance to NS3 and NS5A regions within the 3-year time frame of this long-term follow-up study.

2.1.2 Exploratory (Adult Population Only)

1. **Objective:** To assess liver function using the Model for End-Stage Liver Disease (MELD) and/or Child-Pugh scores in all adult subjects.
2. **Objective:** To assess CKD status by assessing change in estimated glomerular filtration rate (eGFR) in subjects from PN052.
3. **Objective:** To assess complication of CKD by recording new onset diabetes, cryoglobulinemia, cardiovascular disease, and/or neurologic disorders (such as stroke) in subjects from PN052.
4. **Objective:** To assess health outcomes by recording the occurrence of variceal bleeding, ascites, spontaneous bacterial peritonitis, encephalopathy, hepatorenal syndrome, hepatocellular carcinoma, liver or kidney transplantation, and graft rejection in subjects who have undergone liver or kidney transplantation.

2.2 SUBJECT INCLUSION CRITERIA (ADULT AND PEDIATRIC POPULATIONS)

Inclusion criteria apply to both adult and pediatric populations unless otherwise noted.

1. Subjects previously participated in a HCV treatment study and received GZR in the treatment regimen.
2. Subject must enroll in PN017 (Visit 1) within 3 months of the last study visit (e.g. follow-up week [FW] 24) of the prior treatment study in which they received a GZR containing regimen.
3. Subject is male or female 3 years of age or older on day of signing informed consent/assent.
4. Subject or subject's legally acceptable representative provides written informed consent (or written informed assent where applicable). Subjects who have consented for the study may also provide consent/assent for Future Biomedical Research (FBR). However, the subject may participate in PN017 without consenting/assenting for FBR.
5. Starting with AM 03: Adult subject must have received at least 1 dose of a GZR-containing regimen in the prior treatment study and identified as having failed therapy in that study.
6. Pediatric subject must have received at least 1 dose of a GZR-containing regimen and experienced virologic failure with 1 or more associated treatment-emergent RASs at FW12 in PN079.

